4. STATISTICAL METHODS

4.1. Primary Statistical Null Hypothesis

There are hierarchically nested co-primary analyses of the 90-day mRS values between the two arms. For the analysis of the weighted mRS values at 90-days the null hypothesis is that the mean weighted mRS value is equal in the two treatment groups. The alternative hypothesis to be tested is that the mean utility is greater in the Trevo Thrombectomy plus Medical Management (Active) treatment arm than the Medical Management alone (Control). For the analysis of the proportion of subjects functionally independent (mRS 0-2) at 90 days in the null hypothesis is that the probability of a functionally independent subject in each treatment group are equal, with an alternative that the probability of a functionally independent subject on the Active arm is larger than for the control arm.

For each co-primary hypothesis test the analysis is based on a Bayesian analysis. Success will be considered for the weighted mRS co-primary analysis first, and will be declared if the posterior probability of the alternative hypothesis (superiority) is sufficiently large. Only if the weighted mRS co-primary analysis is positive will analysis then proceed to the nested dichotomous analysis. For the nested analysis, success will be declared if the posterior probability of the alternative hypothesis (superiority) is sufficiently large. The threshold for success if no adaptive enrichments are made is 0.986, and this threshold increases if adaptive enrichments occur. The adjusted thresholds are to control type I error and are detailed in the Adaptive Design Plan in Appendix F of Study Protocol.

4.2. Study Success

If the utility-weighted mRS analysis is positive, the study will be considered to have had success in demonstrating benefit in reducing (shifting) disability.

If the utility-weighted mRS analysis is neutral, no further analysis for study success will be performed.

If the utility-weighted mRS analysis is positive, and the nested dichotomous analysis is neutral - the study will be considered to have had success in demonstrating benefit in reducing (shifting) disability but not benefit in increasing functional independence.

If the utility-weighted mRS analysis is positive, and the nested dichotomous analysis is also positive - the study will be considered to have had success in demonstrating benefit in reducing (shifting) disability and also success in demonstrating benefit in increasing functional independence.

4.3. The Secondary Efficacy and Safety Endpoints

For binary outcomes, the count and percentage will be provided for each treatment arm. The difference in the rate between the treatment arms and the 95% CI for the difference will be calculated using the normal approximation to binomial. P-values will be calculated by the Chi-squared test as appropriate. Fisher's exact test is used in place of the Chi-square test when at least one cell count in the 2x2 table has expected value less than 5 or total sample size is less than or equal to 40. The p-value will be denoted with an asterisk (*) in the case where a Fisher's exact test was used.

Relative Risk (RR) was provided as Trevo thrombectomy plus medical management / medical management.

$$SE = \sqrt{\{(1-p_1)/n_{11} + (1-p_2)/n_{21}\}}$$

$$95\% \text{ CI} = RR \cdot \exp(\pm 1.96 \cdot SE).$$

For continuous outcomes, n, mean, median, interquartile (Q3-Q1), standard deviation, minimum, and maximum values will be provided for each treatment arm. P-values will be calculated using a t-test assuming un-equal variances to compare the difference between two treatment arms.

Difference = Trevo thrombectomy plus medical management – medical management.

$$95\% \text{ CI} = \text{Diff} \pm 1.96 \cdot SE$$

$$SE = \sqrt{p_1q_1/n_1 + p_2q_2/n_2} \text{ for proportions,}$$

$SE = \sqrt{[(1/n_1 + 1/n_2)\{(n_1-1)s_1^2 + (n_2-1)s_2^2\}/(N-2)]}$ for continuous variables.

For ordinal variables a Wilcoxon rank sum test will be used and footnoted.

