5.4. Analysis of Secondary Safety Outcome

Both Arms:

- a. Incidence of SICH, by ECASS III definition, within 24 (-6/+24) hours post randomization (time zero) will be presented by providing the count and percentage for each treatment arm. The difference in the percentage between two arms and the 95% CI for the difference will be calculated using the normal approximation to binomial. P-values will be calculated by the Chi-squared test or Fisher's exact test as appropriate. Relative Risk (RR) was provided as Trevo thrombectomy plus medical management / medical management.
- b. Incidence of neurological deterioration from baseline NIHSS score through Day 5-7/discharge (whichever is earlier) post randomization (time zero). Neurological deterioration is defined as ≥ 4 point increase in the NIHSS score from the baseline

STRYKER CONFIDENTIAL - THIS DOCUMENT CONTAINS CONFIDENTIAL AND PROPRIETARY INFORMATION THAT IS THE PROPERTY OF STRYKER CORPORATION. NEITHER THIS DOCUMENT NOR THE INFORMATION HEREIN MAY BE REPRODUCED, USED, OR DISCLOSED TO ANY THIRD PARTY WITHOUT THE PRIOR WRITTEN CONSENT OF STRYKER CORPORATION

score, which will be presented by providing the count and percentage for each treatment arm. The difference in the percentage between two arms and the 95% CI for the difference will be calculated using the normal approximation to binomial. P-values will be calculated by the Chi-squared test or Fisher's exact test as appropriate. Relative Risk (RR) was provided as Trevo thrombectomy plus medical management / medical management.

Treatment Arm:

Incidence of procedure-related and device-related serious adverse events (PRSAEs and DRSAEs) through 24 (-6/+24) hours post randomization (time zero) as adjudicated by the clinical events committee, and defined as:

- a. vascular perforation
- b. intramural arterial dissection
- c. embolization to a new territory
- d. access site complication requiring surgical repair or blood transfusion
- e. intra-procedural mortality
- f. device failure (*in vivo* breakage)
- g. any other complications adjudicated by the CEC to be related to the procedure

The number of Subjects with SAEs will be summarized by CEC adjudicated category described as above, separately by specified categorization, i.e. procedure-related vs. device-related. N, percentage and exact Clopper-Pearson 95% CI of the variables will be provided in each category.

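### SAP 4.3 takes intervals and p-values from different methods, so sparse safety results, mainly SICH, can contradict each other or have no value (minor)

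*SAP*

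**What the plan says.** SAP 4.3 sets the rules for all secondary efficacy and safety endpoints.

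- **Difference of rates.** "the 95% CI for the difference will be calculated using the normal approximation to binomial". The printed standard error is the unpooled one, built on "p_1q_1/n_1 + p_2q_2/n_2", with multiplier 1.96 (a Wald interval).
- **Test of rates.** Chi-squared by default. As for Fisher's method, it "is used in place of the Chi-square test when at least one cell count in the 2x2 table has expected value less than 5". The same switch applies if there are 40 subjects or fewer in all. A Fisher p-value is marked with an asterisk. No change of interval goes with the change of test.
- **Relative risk.** The log-scale standard error divides by n11 and n21, which I read as the event counts in the two arms. No rule is given for zero events.
- **Continuous outcomes.** "P-values will be calculated using a t-test assuming un-equal variances to compare the difference between two treatment arms". The standard error printed for the interval, however, pools the two variances over N − 2 and uses 1.96.

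Sections 4.15.5, 4.15.7, 5.3 and 5.4 repeat the binary rules by endpoint. For SICH, section 5.4 again says that the "95% CI for the difference will be calculated using the normal approximation to binomial". Section 4.15.5 repeats the unequal-variance t-test for infarct size. Exact Clopper-Pearson limits are specified only for rates within the treatment arm. Sections 6.2 and 6.3, on missing data and denominators, do not deal with zero events.

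**The concern.** The SAP recognises that the normal approximation is unsafe for sparse tables, since it changes the test, but it leaves the interval on that approximation. A 95% interval that excludes zero can then be printed beside a p-value above 0.05, and the SAP does not say which one governs. SICH is the outcome most exposed. It is a named secondary safety outcome, and Protocol 12.3 lists comparative SICH rates among the data on which the DMC advises about continuing or stopping. Two further outputs can fail: a zero-width interval when neither arm has an event, and a relative risk that cannot be computed when the control arm has none. The continuous rule has the same mismatch in a milder form.

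**Working it through.** The SAP gives no numerical result for these rules, so there is no stated figure to reproduce. I applied the formulas as printed.

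**Inputs from the documents**
- 1:1 allocation (SAP 3.2). Maximum 250 per arm (SAP 3). Minimum 150 in total, that is 75 per arm (protocol synopsis).
- Illustrative SICH rates: 10% treated and 2% control (Protocol Table 4). The control rate comes from 59 subjects, about one event (0.02 × 59 = 1.2).
- A stop for expected success needs at least 200 subjects (SAP 4.13.3; the thresholds in Protocol 8.6.3 start at 200). Under the pre-specified rules, a stop at 150 can only be for futility (Protocol 8.6.1).

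**Assumptions.** Two-sided 5% level (SAP 4.15.1 states it for baseline comparisons). Sizes of 100 and 150 per arm. Any other event rates, and the SDs, are labelled below.

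**1. One table worked through: 7/100 against 1/100**
- Expected events per arm: (7 + 1)/2 = 4, below 5, so Fisher applies; p = 0.065.
- SE = √(0.07 × 0.93/100 + 0.01 × 0.99/100) = √0.00075 = 0.0274.
- Interval = 0.06 ± 1.96 × 0.0274 = 0.6 to 11.4 points, which excludes zero.

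Other tables:
- 5/100 against 0/100: 0.7 to 9.3 points, p = 0.059.
- 7/250 against 1/250: 0.2 to 4.6 points, p = 0.068. A conflict is therefore possible at full enrolment.
- 0 against 0: SE = 0, so the interval is 0 to 0.

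**2. How often interval and p-value disagree** (exact binomial enumeration, 10% against 2%)

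| Per arm | All disagreements | Involving Fisher | Wald coverage |
|---|---|---|---|
| 75 | 13.8% | 13.8% | 93.7% |
| 100 | 6.2% | 3.1% | 94.4% |
| 150 | 0.3% | about 0.1% | 94.6% |
| 250 | 0 | 0 | 94.8% |

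The rest at 100 per arm is Wald against chi-squared. For example, 8/100 against 2/100 gives 0.02 to 11.98 points. The chi-squared z is 0.06/√(0.05 × 0.95 × 2/100) = 1.95, so p = 0.052.

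Sensitivity to assumed rates: at 5% against 2%, disagreements involving Fisher are 12.5%, 7.7% and 0.1% of trials at 75, 100 and 250 per arm. At 1% in both arms they are 3.7% at 250.

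**3. Relative risk.** With no control events the ratio has a zero denominator. At a 2% control rate the probability is 0.98^75 = 22%, 0.98^100 = 13% and 0.98^250 = 0.6%. With no treated events the ratio is 0 and its standard error is infinite.

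**4. Continuous outcomes.** With n per arm, the pooled variance of the difference is (2/n) × (n − 1)(s1² + s2²)/(2n − 2) = (s1² + s2²)/n, which is the Welch variance. With assumed SDs of 30 (treated) and 60 (control):
- 75/75: both SEs are 7.746. Only 1.96 against t = 1.982 differs, so the printed half-width is about 1% short.
- 110/90: pooled 6.535, Welch 6.941 (6% too small).
- 90/110: pooled 6.943, Welch 6.537 (6% too large).

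**5. Would a better interval alone be enough?** No. The Miettinen-Nurminen statistic at zero difference is z = 2.16 for 7 against 1 per 100, and z = 2.02 for 4 against 0 per 100. Both score intervals exclude zero beside Fisher p = 0.065 and 0.12. With Fisher kept, total disagreement falls only from 13.8% to 12.7% at 75 per arm and from 6.2% to 3.1% at 100.

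**The case against.** The other side has a good deal to say. These are secondary and safety summaries; SAP 4.5 calls additional endpoint analyses supportive, without alpha control. Each Fisher p-value is flagged, and counts and percentages are always shown, so a reader can see a sparse table. The primary safety outcome is stroke-related mortality. Protocol Table 4 gives all-cause 90-day mortality of 25–27%, so even 75 per arm would carry about 0.25 × 75 ≈ 19 deaths, and chi-squared would normally apply. For infarct size, SAP 4.15.5 asks for descriptive statistics and a p-value and does not itself call for an interval.

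Most of this stands, and it limits the weight of the point. It does not remove it: lack of alpha control concerns multiplicity and does not justify two outputs that contradict each other or one that cannot be computed.

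Three stronger readings are tempting and not supported:
- A reader might infer that the 75-per-arm figures (13.8% and 22%) apply to a trial that supports the wider time window. Under the pre-specified rules a trial of that size has stopped for futility.
- A reader might infer that the SICH intervals badly undercover. At 10% against 2%, coverage is 93.7% or better at every size run. It falls to 89% at 75 per arm and 92% at 150 only at assumed rates of 3% and 1%, which the documents do not give.
- A reader might infer that the pooled standard error makes intervals too narrow. The error can go either way and needs both arm sizes and SDs to differ.

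**Conclusion.** The mismatch is on the page in SAP 4.3, and nothing elsewhere in the SAP cures it. Its practical reach is narrow: rare between-arm outcomes, mainly SICH, in a trial that stops early. At 10% against 2%, interval and p-value disagree in about 6% of trials at 100 per arm (half of that involving Fisher), 0.3% at 150 and none at 250. The relative risk has no value in 13% of trials at 100 per arm and 0.6% at 250 if the control rate is 2%. The continuous mismatch is about 1% of the half-width or less with equal arms in the cases run. These sizes depend on SICH rates borrowed from cited cohorts; lower rates would keep some disagreement at larger sizes. The Bayesian co-primary analyses are unaffected and stroke-related mortality is little affected. The severity is minor.

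**What to change.** Amend SAP 4.3, and align 4.15.5, 4.15.7, 5.3 and 5.4, before data lock (SAP section 1 allows revision until then).

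1. **Rates.** For each between-arm comparison take the interval and the p-value from one method: either the Miettinen-Nurminen score interval with its matching score test, or an exact unconditional interval with its matching exact test. Either choice replaces the switch between chi-squared and Fisher and its asterisk. Changing the interval while keeping Fisher would leave the conflict in place.
2. **Relative risk.** State that with zero events in an arm it is reported as not estimable, with either a one-sided score limit or the risk difference only.
3. **Continuous differences.** Use the Welch standard error with the Satterthwaite t quantile.

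The cost is SAP wording and SAS options; no new data are needed. The downside is that some sparse-event intervals become slightly wider.

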4.4. Comparability Analyses of the Patient Populations

These analyses are intended to determine the similarity of treatment groups and study sites with respect to important demographic or other variables, either known or suspected to have an influence on the outcome variables. The absence of similarity for any baseline variable will identify that variable as a potential covariate in subsequent safety and effectiveness multivariable analyses. The data for each baseline variable will be presented descriptively. For quantitative variables like age, the mean, standard deviation (SD), median, minimum, and maximum will be presented. For qualitative variables like gender, the number with the characteristic, the total number evaluated, the rate, and the exact 95% binomial confidence limits will be presented.

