Study Objective				
Primary Objective	To evaluate the hypothesis that Trevo thrombectomy plus medical management leads to superior clinical outcomes at 90 days as compared to medical management alone in appropriately selected subjects experiencing an acute ischemic stroke when treatment is initiated within 6-24 hours after last seen well.			
Secondary Objective(s)	To provide evidence that endovascular reperfusion with Trevo is associated with a significant reduction in median infarct size compared to the control group at 24 (-6/+24) hours post randomization.			
Test Device	Trevo [®] ProVue [™] and Trevo [®] XP ProVue [™] Retrievers			
	Study Design			
Study Design	Prospective, randomized, multi-center, Phase II/III (feasibility/pivotal), adaptive, population enrichment, blinded endpoint, controlled trial.			
Planned Number of Subjects	A maximum of 500 subjects is planned to be enrolled; 250 in the Treatment arm and 250 in the Control arm. The minimum sample size is 150 subjects.			
Planned Number of Sites / Countries	Worldwide (up to 50 sites). No more than 20 sites will be outside of the U.S.			
Primary Endpoint	90-day disability assessed by the modified Rankin scale (mRS)			
Secondary Endpoints	 Proportion of subjects with a good functional outcome at 90 days, defined as mRS 0-2 Proportion of subjects with "early response" at Day 5-7/Discharge (whichever is earlier), defined as a NIHSS drop of ≥10 points from baseline or NIHSS score 0 or 1 Difference in all cause mortality rates between the two groups. Difference in median final infarct size at 24 (-6/+24) hours from randomization, by MRI T2/Flair or CT (if contraindicated for MR) Difference in revascularization rates at 24 (-6/+24) hours from randomization, by CT-MR core lab assessment of vessel patency on CTA/MRA. Treatment Arm Only: Analysis of vessel reperfusion rates (percentages) post device and post procedure, by angiography core lab measurement of modified TICI ≥ 2b 			

Document Number: CDM10000146

Rev: AD

Primary Safety Outcome	Both Arms: 1. Incidence of stroke-related mortality at 90 days					
Secondary Safety Outcomes	 Both Arms: Incidence of SICH, by ECASS III definition, within 24 (-6/+24) hours post randomization (time zero) Incidence of neurological deterioration from baseline NIHSS score through Day 5-7/discharge (whichever is earlier) post randomization (time zero). Neurological deterioration is defined as ≥ 4 point increase in the NIHSS score from the baseline score. 					

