Statistical Test Method	The alternative hypothesis is that the proportion of subjects functionally independent (mRS 0-2) and the average of the weighted mRS categories at 90 days in the Trevo Thrombectomy plus Medical Management group is superior to Medical Management alone. The final analysis is a Bayesian analysis of the 90-day mRS scores, and declares success if there is sufficiently large posterior probability that the overall treatment effect is positive. The threshold for success if no enrichments are made is 0.986, and this threshold increases as the enrichment becomes earlier and more aggressive. The adjusted thresholds are to control type I error. Enrichment decisions and early stopping rules are based on Bayesian predictive probabilities outlined in the Adaptive Design Plan in Appendix F .

Document Number: CDM10000146

Rev: AD

Sample Size Parameters	The sample size for the trial is assessed through simulation, which considered effect sizes ranging from zero to a 1.5 increase on the weighted mRS scale. For one-sided Type I error probability of 2.5%, the design has 86% power for a 1 unit increase in weighted mRS.

Document Number: CDM10000146

Rev: AD

1	Intro	duction and Rationale	13		
	1.1	Incidence and Burden of Stroke	13		
	1.2	Current Treatment Options	13		
	1.3	Unmet Need in Acute Ischemic Stroke	13		
	1.4	Purpose of Study	15		
2	Study	7 Device	15		
	2.1	Study Device Description	15		
	2.2	Study Device Labeling	17		
3	Study	Study Objective			
	3.1	Primary Objective	18		
	3.2	Secondary Objectives	18		
4	Study	7 Endpoints and Safety Outcomes	18		
	4.1	Primary Endpoint	18		
	4.2	Secondary Endpoints	19		
	4.3	Primary Safety Outcome	19		
	4.4	Secondary Safety Outcomes	19		
5	Study	Study Design			
	5.1	Overview	20		
	5.2	Justification for the Study Design	22		
		5.2.1Justification for Expansion of Time Window			
		5.2.2Justification for Inclusion of Wake up and Unclear Onset Strokes			
		5.2.3Justification for Inclusion of IV tPA Failures			
		5.2.4Justification for Non Reliance on Penumbra Imaging			
		5.2.5Justification for Use of Clinical Imaging Mismatch Criteria			
		5.2.6Justification for Use of Standardized Core Infarct Imaging Software			
		5.2.7Justification for Use of Weighted mRS as Primary Endpoint			
		5.2.8Justification for Use of Adaptive Design			
	5.3	Method of Assigning Subjects to Treatments			
	5.4	Blinding and Breaking the Blind	33		
6	Study	Study Population			
	6.1	- Inclusion Criteria	34		

Document Number: CDM10000146

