8.7 Statistical Analysis

The final weighted and dichotomous analyses will be performed only on the enriched population, and assumes a constant treatment effect over all infarct sizes that are in the population at the end of the trial.

The trial is considered successful if there is sufficiently high posterior probability that the treatment effect is positive. The threshold for success is adjusted to account for the degree to which the population has been enriched, and depends on the following factors:

- The number of enrolled subjects in the enriched population at the time of the enrichment decision (N_1)
- The number of enrolled subjects outside the enriched population (N_2)
- The number of subjects enrolled after the enrichment decision (N_3) .

Specifically, the threshold is calculated as:

Document Number: CDM10000146

Rev: AD

$$\Phi(\sqrt{1+\frac{N_2}{N_1+N_3}}\Phi^{-1}(p_{crit})),$$

where Φ is the standard normal cumulative distribution and $p_{crit} = 0.986$ is a critical probability evaluated via simulation to control Type I error probability. If no enrichments are made during the trial, then the success threshold is equal to p_{crit} , and the threshold increases as enrichment becomes earlier and more aggressive.

The primary analysis of mRS scores for the interim and final analyses will be performed by Berry Consultants, LLC using custom code developed in Java and R software.

The Secondary efficacy and safety analyses will be performed by Stryker NV Biostatistics personnel using SAS, version 9.2 or higher. Pooling of data across institutions and stratification will be described in the Statistical Analysis Plan.

8.7.1 **Baseline Comparability**

Baseline comparability between the two arms will be done using descriptive statistics and will be described in detail within the Statistical Analysis Plan.

8.7.2 **Pooling Across Institutions**

Results for the primary efficacy endpoint will be presented by site and treatment group. Poolability across institutions will be assessed using an ANCOVA on the weighted mRS with terms for treatment group, site, and the interaction of treatment group and site. A p-value less than 0.10 for the interaction term will be taken as evidence that there are significant differences in treatment effect between sites. If the effect is found to vary by site, then the effect will be analyzed using a hierarchical model with random site effect.

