3.2. Randomization

Subjects will be randomized 1:1 to Trevo thrombectomy plus medical management or medical management alone.

Stratification will occur by: Clinical Imaging Mismatch (CIM) subgroup (see Imaging Inclusion Criteria), Time Last Seen Well (TLSW) ≥ 6 to ≤ 12 hours vs. >12 to ≤ 24 hours, and Baseline Occlusion Location (ICA vs. M1). Blocks will be assigned to all sites including the stratification mapping to maintain balance at all sites.

After randomization, no crossover is permitted.

Enrollment in this study is defined as the moment when the randomization process is completed and the subject is assigned to a study arm. In case of any protocol violations all efficacy analyses will be based on an intent-to-treat analysis where subjects are classified by the group in which they are randomized.

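### The secondary and safety comparisons leave out the stratification factors, and covariates for the supportive models are nominated by observed imbalance; this costs precision but does not inflate type I error

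*SAP*

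**What the plan says.** SAP 3.2 sets the allocation: "Subjects will be randomized 1:1 to Trevo thrombectomy plus medical management or medical management alone". It then says "Stratification will occur by: Clinical Imaging Mismatch (CIM) subgroup", and adds TLSW (up to 12 hours against later) and occlusion location (ICA against M1). It also says that blocks go to all sites with the stratification mapping.

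SAP 4.3 gives the general method for secondary efficacy and safety. For binary outcomes, "P-values will be calculated by the Chi-squared test as appropriate", with Fisher's test for small counts. Continuous outcomes get an unequal-variance t-test and ordinal ones a Wilcoxon test. SAP 4.15.5, 5.3 and 5.4 apply the binary tests and the t-test outcome by outcome, and none of these comparisons carries a stratum term. The poolability ANCOVA in SAP 4.15.6 contains arm, site and their interaction only.

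Protocol 8.7 says: "Pooling of data across institutions and stratification will be described in the Statistical Analysis Plan". The SAP describes the strata in the randomisation section and lists all three factors as subgroups in SAP 4.5. It specifies no stratified or stratum-adjusted treatment estimate.

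On covariates, SAP 4.4 says: "The absence of similarity for any baseline variable will identify that variable as a potential covariate". SAP 4.5 classes multivariate analyses as supportive, without alpha control.

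**The concern.** When randomisation is stratified on factors related to outcome, an analysis that leaves them out uses a standard error that still contains the between-stratum variance. If the arms are balanced within strata, that variance does not contribute to the treatment difference, so the interval is too wide and the test conservative. If they are not well balanced, the standard error is about right, but the estimate is noisier than it need be. Precision is lost either way. For stroke-related mortality and symptomatic haemorrhage, a conservative test is not the cautious direction, because it makes an excess of harm slightly harder to see.

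The rule in SAP 4.4 is a separate weakness. In a randomised comparison, observed imbalance is a poor reason to adjust; relation to outcome is the good one. Stratification tends to balance the factors the sponsor thought most important, so an imbalance rule tends to pass over them and pick up chance differences. With no cutoff and no list, the supportive models cannot be fixed before the data are seen.

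**Working it through.** **1. The plan's own figure.** The protocol synopsis says: "For one-sided Type I error probability of 2.5%, the design has 86% power for a 1 unit increase in weighted mRS", and "A maximum of 500 subjects is planned to be enrolled; 250 in the Treatment arm and 250 in the Control arm". The control mRS proportions (SAP Table 1) sum to 0.99. Rescaled and combined with the utility weights 10, 9.1, 7.6, 6.5, 3.3, 0, 0, they give a mean of 4.56/0.99 = 4.606 and an SD of 3.631. For a fixed sample of 250 per arm:

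- SE = 3.631 × √(2/250) = 0.325
- power = Φ(1/0.325 − 1.96) = Φ(1.12) = 86.8%

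This reproduces 86% at one-sided 2.5%. SAP 4.1 says: "The threshold for success if no adaptive enrichments are made is 0.986". At the corresponding one-sided 1.4%, the same calculation gives 81.1%. The plan's figure comes from adaptive simulations that cannot be rerun without Appendix F, so this is only a check on the inputs.

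**2. Effect of omitting the strata, arms balanced within strata.** Let R² be the share of outcome variance explained by the strata (assumed, not in the documents).

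- SE overstatement = 1/√(1−R²) − 1
- true one-sided error of a nominal 2.5% test = 1 − Φ(1.96/√(1−R²))

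| R² | SE overstated by | True one-sided error |
|---|---|---|
| 5% | 2.6% | 2.2% |
| 10% | 5.4% | 1.9% |
| 20% | 11.8% | 1.4% |
| 30% | 19.5% | 1.0% |

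**3. How balanced the strata will be.** There are 3 × 2 × 2 = 12 strata. Run centrally, 500 subjects give about 42 per stratum and balance is good. If blocks are held within each of up to 50 sites (SAP 3 and 3.2), there are 12 × 50 = 600 cells for at most 500 subjects, and most blocks stay incomplete.

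**4. Simulation of both cases.** N = 500, 3,000 runs per setting, with block size 4 and the stratum shares assumed. The Monte Carlo error is about 1.3% on an SD and about 0.3 percentage points on an error rate (√(0.025 × 0.975/3000) = 0.0029).

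| R² | Central: unadjusted SE / true SD | Central: one-sided error | 50 sites: unadjusted SE / true SD | 50 sites: one-sided error | 50 sites: adjusted SD / unadjusted SD |
|---|---|---|---|---|---|
| 10% | 1.054 | 1.9% | 1.018 | 2.3% | 0.972 |
| 20% | 1.124 | 1.4% | 1.031 | 2.2% | 0.932 |
| 30% | 1.214 | 1.0% | 1.065 | 1.9% | 0.883 |

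The central case matches the formula. With 50 sites most of the overstatement disappears, but adjustment then lowers the true SD by about 3%, 7% and 12%. In that case the adjusted model's own SE ratios were 0.997, 0.992 and 1.012. The width of an unadjusted interval relative to an adjusted one is therefore:

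- R² 10%: 1.018/(0.997 × 0.972) = 1.05
- R² 20%: 1.031/(0.992 × 0.932) = 1.12
- R² 30%: 1.065/(1.012 × 0.883) = 1.19

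These are close to 1/√(1−R²). The randomisation scheme decides where the loss appears, not how large it is.

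**5. The imbalance rule.** SAP 4.4 gives no cutoff. SAP 4.15.1 plans baseline tests at two-sided 0.05, though SAP 4.4 does not refer to them. If that were the trigger, and the 18 to 20 variables listed there were independent, the chance of at least one false flag would be 1 − 0.95¹⁸ = 60% to 1 − 0.95²⁰ = 64%.

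**The case against.** The strongest reply is that nothing decisive is affected. Any error in the specified tests is conservative. SAP 4.4 looks only at variables known or suspected to influence outcome, and makes a dissimilar one no more than a potential covariate. SAP 4.5 makes the resulting models supportive. The three factors are also pre-specified as subgroups. All of this stands and limits the consequences. It does not supply an adjusted estimate, since subgroup results are not adjustment, and it does not give the supportive models a fixed form.

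Four stronger readings are tempting, and the documents do not support them.

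- A reader might infer that the primary analysis also ignores the strata, especially as a plain two-sample calculation reproduces 86%. The SAP states no covariates for that model either way and defers its details to Appendix F; the match cannot settle the question.
- A reader might take the 12% at R² 20% as the overstatement of the standard error. That needs near-perfect stratum balance. With blocks inside 50 sites it is about 3%, and a second simulation with 25 sites gave 4% to 5%.
- A reader might see a broken promise in Protocol 8.7. That sentence can be read as satisfied by SAP 3.2 and 4.15.6, because it does not commit to a stratified analysis.
- A reader might treat all three factors as established predictors. Protocol 5.2.5 supports core volume and age, and Protocol 1.3 expects worse outcomes with more proximal occlusion and later arrival. The studies in Protocol 5.2.1 disagree about time.

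A practical objection also stands. Twelve strata are too many for uncommon safety events. Enrichment to 0–30 cc would remove the CIM group with 31 to under 51 cc from the secondary efficacy population (SAP 4.13.2 and 4.15.5).

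**Conclusion.** The point holds for the two-arm secondary efficacy and safety comparisons and for the supportive multivariable models. The comparisons omit the stratification factors, and the covariate rule depends on the data. Reported intervals are about 5% wider than stratum-adjusted ones if R² is 10%, and about 12% wider if it is 20%. With well-balanced strata, the true one-sided error of a nominal 2.5% test is about 1.9% and 1.4%. With blocks within up to 50 sites it is about 2.3% and 2.2%, and the rest of the loss is efficiency.

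These sizes rest on an assumed R², an assumed block size and assumed stratum shares. Type I error is not inflated, and no effect on the success criterion is shown. The change is worth making because it uses data already collected, but the trial's main conclusion is not shown to depend on it.

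**What to change.** 1. Replace the SAP 4.4 sentence with: *Adjusted analyses use the pre-specified covariates CIM subgroup, TLSW stratum and occlusion location; observed baseline imbalance is not used to select covariates.*
2. In SAP 4.3 and 4.15.5, report Mantel-Haenszel risk differences with Cochran-Mantel-Haenszel tests for binary secondary efficacy outcomes, stratified by CIM and TLSW (3 × 2 = 6 cells). Add occlusion location only if a numerical minimum cell size, fixed before unblinding, is met. Use only the CIM levels that remain after any enrichment.
3. For 24-hour infarct size, use a van Elteren rank test stratified by the same factors, with a supportive ANCOVA on transformed volume adjusting for baseline core volume. Core volume is already measured before randomisation (Protocol 7.2).
4. Keep the unadjusted or exact test for uncommon safety events, and report a stratified estimate where counts allow.
5. Add a strata-adjusted supportive analysis of the weighted and dichotomous mRS.

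The cost is SAP wording and a small amount of programming. The downside is that stratified estimates can be unstable when events are sparse, which is why items 2 and 4 limit their use.
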